11.3 Statistical criteria of termination of trial

Not applicable. In brief, we do not have statistical criteria of early termination of the trial. Safety will be monitored by the independent DSMB (which includes patient representatives). If the DSMB observes a major safety concern (i.e. which would also be unacceptable if linezolid is superior to compared to standard of care) the DSMB will have the power to initiate the early termination of the trial.

11.4 Planned Analyses

11.4.1 Datasets to be analysed, analysis populations

Analyses will be performed on the full analysis set (i.e., all randomised participants) and the per protocol dataset

(i.e., those who received at least 7 out of 10 doses of linezolid or placebo). The primary estimand to be calculated in this study is the effect (summarised as the win ratio) of being randomly assigned to treatment with linezolid in the patient population (i.e., equivalent to an intention-to-treat analysis). We will also estimate the treatment effect among the treated participants (i.e., the per protocol dataset).

A detailed analysis plan will be written before closing the study database. Of note, we are currently conducting a systematic scoping review, assessing current practices how to analyse a hierarchical composite outcome. These results will inform our pre-specified analysis plan. Furthermore, we will consider further developments in risk-score classifications for *S. aureus* bacteraemia (e.g. for a potential use of a matched win-ratio versus unmatched win-ratio). The statistical analysis plan will be made publicly available (on clinicaltrials.gov). Currently we intend to conduct the following analyses:

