3.7 Risks / Benefits

Risks

The most commonly reported adverse event of linezolid is gastrointestinal intolerance, occurring in approximately 30-40% of patients when linezolid is administered for a longer duration.^{72 73} Within the first 5 days of treatment, gastrointestinal intolerance manifests in approximately 8% leading to early discontinuation in 3%.⁷³ Myelosuppression, which primarily presents as thrombocytopenia, is another common adverse effect of linezolid that affects up to a third of patients⁷⁴⁻⁷⁷ and occurs more frequently during treatment durations of ≥ 10 days.^{74 78} Moreover, linezolid is a weak, reversible, and unselective monoamine oxidase inhibitor.⁷⁹ Consequently, the combination of linezolid with other serotonergic drugs, such as selective serotonin reuptake inhibitors (SSRIs) or tricyclic antidepressants, can potentially lead to an increase in serotonin activity. The clinical effects of serotonin excess can range from mild serotonin-related side effects to severe serotonin toxicity.^{80 81} In the largest meta-analysis involving 2208 patients receiving linezolid and 5058 patients not receiving linezolid, the observed incidence of serotonin toxicity was 0.4% among patients taking linezolid in combination with a serotonergic agent (compared to 0.15% in those taking a serotonergic agent alone).⁸² Similarly, in a large cohort of 1135 patients, fewer than 0.5% experienced serotonin toxicity.⁸³ Further, hyperlactataemia is a rare but potentially severe adverse effect of linezolid documented in various case reports.^{72 84 85} The incidence is not well reported, but may be at 1-3% according to retrospective studies.^{73 86} Finally, it should be noted that linezolid can potentially cause peripheral and/or optic neuropathy if treatment is administered for more than 28 days.^{85 87} Given the short treatment duration of 5 days, we expect a low incidence of these adverse events in our study. Nevertheless, we will closely monitor the administration of the drug and, if necessary, terminate treatment in response to adverse events (see 8.6 *Trial specific preventive measures*).

Benefits

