DOOR comprises five ranks (Table 3: Desirability of Outcome Ranking (DOOR) outcome used for the LIPS trial). This outcome is assessed at day 90. The overall distribution of rankings can then be compared between the control and intervention arms, with the final treatment effect estimate being the win ratio, i.e., the probability that a participant randomly assigned to the intervention arm has a superior DOOR compared to a participant randomly assigned to the control arm⁹⁹ (see section 11 STATISTICAL METHODS).

Rank	Alive at 90 days	Return to usual level of function by day 90	None of the following complications:	Hospital length of stay
1	Yes	Yes	Yes (no complications occurred)	Ties will be resolved using the length of hospitalisation
2	Yes	Yes	No (complication occurred)	
3	Yes	No	Yes (no complications occurred)	
4	Yes	No	No (complication occurred)	
5	No	Not applicable	Not applicable	Not applicable

Table 3: Desirability of Outcome Ranking (DOOR) outcome used for the LIPS trial

Detailed definitions of DOOR components:

Alive at 90 days: defined as alive at 90 days after randomisation

Return to usual level of function by day 90: defined as return to baseline value (or better score) according to the modified functional bloodstream infection score¹⁰⁴. Baseline is defined as the best score within the 4 weeks before randomisation. The scores used will be the following:

- 6: Out of hospital, able to complete daily activities without assistance (no limitations)
- 5: Out of hospital, able to complete daily activities without assistance but with some limitations (e.g. slow, pain)
- 4: Out of hospital, unable to complete daily activities without assistance
- 3: Out of hospital; significant disability; requires a high level of care and assistance daily (this includes residential

aged care and nursing homes)

2: Hospitalised (or equivalent)

1: On palliative care in terminal phases of life (in hospital or at home)

Complications:

- Microbiological or clinical failure leading to treatment change: This includes any type of adaptation of the treatment such as new intervention or surgery, or re-start, prolongation or change of antibiotic treatment

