 - Microbiological failure: Any positive sterile site culture with *S. aureus* between 14 and 90 days after randomisation. A sterile site means any site of the body where microorganisms are usually absent, i.e. below the outer and inner colonised surfaces of the skin and mucous membranes. Positive sterile sites cultures include deep visceral and musculoskeletal abscesses obtained in a sterile manner.
 - Clinical failure: Newly identified focus of *S. aureus* between 14 and 90 days after randomisation as determined by the site investigator (or delegated physician). This can incorporate clinical, radiological, microbiological and pathological findings.
- Serious adverse reaction (SAR, see definition below)
- Any adverse event (irrespective of grade) leading to study drug discontinuation

Hospital length of stay: This corresponds to the duration of the index acute hospital stay from randomisation until the day of hospital discharge. Transfers to another acute care hospital for continuation of acute treatment will be included in the assessment of hospital length of stay. Days after transfer to rehabilitation centres or switch to outpatient parenteral ambulatory treatment will not be included in the acute hospital stay.

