7.4 Criteria for withdrawal / discontinuation of participants

Participants can withdraw from the study at any time without providing a reason. Participants who discontinue the intervention will still be encouraged to complete follow-up assessments. Reasonable effort should be made to

establish the reason for discontinuation while fully respecting the participant's rights so reasons may be analysed. In case of adverse events, the treating physician decides (if possible, together with participants or close relatives) whether the study drug must be discontinued. Outcomes of these participants will still be collected, and they remain in the intention-to-treat analysis as randomised.

Participants who were included after receiving consent from their next of kin or confirmation by an independent physician will be asked to provide retrospective consent as soon as their health status allow an informed decision. If the participant refuses to give this retrospective consent, we will not collect any further data. However, we will analyse the data that has been collected up to this timepoint, as excluding these data could bias the analysis.

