8.3 Dose modifications

Drug-related AEs leading to discontinuation of the drug are expected to be extremely rare when linezolid is used for 5 days. Discontinuation of IMP may occur in the situations listed in chapter 6.4 *Unblinding Procedures (Code*

break) and chapter 7.4 *Criteria for withdrawal / discontinuation of participants*. The study medication will be given twice a day for 5 days (in total 10 administrations) with approx. 12 hours interval between each administration. If maintaining a fixed 12-hour interval is challenging due to the start time (e.g. if subsequent doses would need to be administered in the middle of the night), the treating physician may adjust the first dosing interval according to standard practice. However, the interval should not be shortened or extended by more than 6 hours. Further dose modifications are not allowed.

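### The per-protocol set (at least 7 of 10 doses, no exceptions) is selected on components of the DOOR, so its win ratio is not an effect among the treated; the direction of the distortion cannot be predicted

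*Protocol*

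**What the plan says.** Protocol 11.4.1 names two analysis sets. The full analysis set is all randomised participants, and the primary estimand, the win ratio by assigned arm, is described as "equivalent to an intention-to-treat analysis". The per-protocol set is "those who received at least 7 out of 10 doses of linezolid or placebo". No exception is made for death or for stopping because of an adverse event. The section continues: "We will also estimate the treatment effect among the treated participants (i.e., the per protocol dataset").

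Section 5.1 defines the outcome. The first component is "Alive at 90 days: defined as alive at 90 days after randomisation", and death by day 90 is rank 5, the worst. The complications domain includes "Any adverse event (irrespective of grade) leading to study drug discontinuation". A survivor with a complication is rank 2 or rank 4, depending on function.

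Section 7.4 says of participants who stop the drug for an adverse event that "they remain in the intention-to-treat analysis as randomised". Section 8.3 fixes the timing: "in total 10 administrations) with approx. 12 hours interval between each administration".

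On the frequency of early stopping, section 3.7 says that within the first 5 days of linezolid "gastrointestinal intolerance manifests in approximately 8% leading to early discontinuation in 3" per cent. Section 8.3 expects drug-related adverse events leading to discontinuation to be extremely rare over 5 days. Section 3.5 expects the greatest benefit of linezolid in the first three days after detection of the infection.

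**The concern.** A per-protocol set defined only by doses taken is formed after randomisation. Here the reasons for missing doses include two events that the DOOR itself scores. A participant who dies before dose 7 is a rank 5 outcome that the set never sees. A participant who stops before dose 7 for an adverse event has a complication that the set never sees. The DOOR is meant to weigh harm together with benefit, and this rule takes early harm out of the balance.

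The label adds to the problem. Participants who took one to six doses of linezolid were treated, but are not in the set. Those who remain in the two arms need not be comparable, because different events may have removed people from each arm. A per-protocol win ratio that differs from the intention-to-treat result could then be taken as evidence about the drug when it reflects who was removed.

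**Working it through.** The protocol gives no figure for the size of the per-protocol set or for its win ratio, so there is none to reproduce.

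**When dose 7 falls.** Six intervals of 12 h give 6 × 12 = 72 h after dose 1. Section 8.3 lets the first interval move by up to 6 h, so the range is 66 to 78 h. Deaths and stops before this point are excluded; those after it stay in. The window overlaps the period in which section 3.5 expects most benefit.

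**How many stops.** If the 3% in 3.7 applied in full before dose 7, 0.03 × 303 = 9.1 linezolid participants would leave for gastrointestinal intolerance. The 3% covers 5 days, so fewer may leave. On the wording of 8.3 the number is close to zero.

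**Hand check A: more stopping on linezolid, no efficacy.** From 11.2, control rates in both arms: death 22.5%, worse function 25.0%, other complications 6.3%. Assume adverse-event stopping before dose 7 of 3% against 0%, and equal early death. Length of stay splits the remaining pairs evenly, ignoring exact ties.
- Linezolid complications: 1 − 0.97 × 0.937 = 9.11%; placebo 6.3%.
- Pairs decided by death: 0.225 × 0.775 = 0.1744 each way. Both alive: 0.775² = 0.6006.
- Decided by function: 0.6006 × 0.25 × 0.75 = 0.1126 each way. Tied on function: 0.6006 × 0.625 = 0.3754.
- Decided by complications: linezolid wins 0.3754 × 0.063 × 0.9089 = 0.0215; loses 0.3754 × 0.0911 × 0.937 = 0.0320.
- Length of stay: (0.3754 − 0.0215 − 0.0320)/2 = 0.1609 each way.
- Full-set win ratio: (0.1744 + 0.1126 + 0.0215 + 0.1609)/(0.1744 + 0.1126 + 0.0320 + 0.1609) = 0.4694/0.4800 = 0.978.
- In the per-protocol set the stoppers are gone, the arms are identical, and the win ratio is 1. The tolerability harm has disappeared.

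**Hand check B: linezolid prevents early deaths.** Total death is 20.3% against 22.5% (11.2). Assume the whole difference arises before dose 7, with early death 2.8% against 5.0%, and everything else equal.
- Full set: wins on death 0.225 × 0.797 = 0.1793; losses 0.203 × 0.775 = 0.1573. Both alive 0.797 × 0.775 = 0.6177, split evenly at 0.3088. Win ratio 0.4881/0.4661 = 1.047.
- Per-protocol deaths: linezolid (0.203 − 0.028)/0.972 = 18.0%; placebo (0.225 − 0.050)/0.950 = 18.4%. Wins 0.1842 × 0.8200 = 0.1510; losses 0.1800 × 0.8158 = 0.1469. Both alive 0.6689, split at 0.3345. Win ratio 0.4855/0.4813 = 1.009.
- A real early survival benefit has been largely removed.

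**Simulation over more settings.** It used 2 million participants per arm (Monte Carlo error about 0.002) and no missing data. The protocol does not give the length-of-stay parameters, so stay was assumed log-normal with median 16 days and log-SD 0.7, longer with a complication. Rates of early death, of stopping, and of frailty among stoppers are assumptions; only the 3% comes from the protocol. Arms are given as linezolid against placebo.

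| Setting | Full set | Per-protocol |
|---|---|---|
| No efficacy, early death 3% in both, stops 1% in both | 0.998 | 0.998 |
| No efficacy, early death 3% in both, stops 3% v 0% | 0.977 | 0.999 |
| Same, stops 3% v 1% | 0.987 | 1.002 |
| Same, stops 3% v 0%, stoppers at twice the later risk | 0.988 | 1.023 |
| Same, stops 5% v 1%, stoppers at twice the later risk | 0.985 | 1.032 |
| Mortality benefit all early (2.8% v 5.0%), stops 1% in both | 1.048 | 1.009 |
| Same, stops 3% v 1% | 1.031 | 1.008 |
| Early mortality harm (5.0% v 2.8%), stops 1% in both | 0.955 | 0.991 |
| Planned effects, early death 3% in both, stops 3% v 1% | 1.247 | 1.289 |
| Planned effects, early death 1.5% v 3.7%, stops 3% v 1% | 1.243 | 1.234 |
| Planned effects, early death 1.5% v 3.7%, stops 1% in both | 1.269 | 1.236 |

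The hand checks agree with the second and sixth rows. Excess stopping on linezolid, with early death equal, raises the win ratio by 0.015 to 0.047. Removing early deaths, with stopping equal, lowers it by 0.033 to 0.039 when linezolid prevents them and raises it by 0.036 when linezolid causes them.

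**The case against.** The strongest defence is that nothing decisive rests on this set. The primary estimand covers all randomised participants, adverse-event stoppers stay in it, and no section gives the per-protocol result a confirmatory role. Section 11.4.1 also leaves detail to a later analysis plan. The first part stands and limits the weight of the point. The second helps less, because the protocol has already fixed both the rule and the label.

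A reader might infer that the set is biased towards linezolid, since drug-caused stops should be commoner on linezolid. The documents do not support that as an overall conclusion. The dose rule applies to both arms, so early placebo deaths go too, and on the trial's own hypothesis of early benefit their removal works against linezolid. Nor would placebo necessarily have no stops: the DOOR counts adverse events of any grade and any cause, in blinded, acutely ill participants.

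A reader might also subtract the 3% in 3.7 from the planned 5.0% linezolid complication rate, leave placebo at 6.3%, and report a large spurious reduction. That shows no bias. It assumes that all other complications run at 2.0% against 6.3% in the full set, so the difference is in the inputs. It also puts every stop before dose 7, ignores 8.3, and looks at the third DOOR domain instead of the win ratio.

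Finally, keeping deaths and adverse-event stoppers does not turn the set into a causal contrast, because excluding other non-adherers is still selection after randomisation. That is correct, and the fix says so.

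**Conclusion.** The point holds for a supplementary analysis. As written, the per-protocol set conditions on early death and early adverse-event stopping, both DOOR components, and its win ratio should not be called the treatment effect among the treated. This follows from 5.1, 8.3 and 11.4.1 and needs no assumption about rates.

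Size and direction do depend on assumptions. Under the rates tried, the per-protocol win ratio differed from the full-set value by up to about 0.05, in either direction, and not at all when early death and stopping were equal between arms. The shift can carry a value across 1 (0.988 to 1.023). With both mechanisms present they can largely cancel or either can dominate, so the sign cannot be known in advance.

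The set does not remove every death or stopper, only those before dose 7. A surviving stopper is rank 2 or 4, not the worst outcome. The intention-to-treat result is untouched.

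**What to change.** In 11.4.1, state that participants in either arm whose doses were missed because of death or an adverse event stay in the per-protocol set, and that only other non-adherence leads to exclusion. Replace the description as an effect among the treated with a supportive per-protocol analysis, noting that it still selects on post-randomisation adherence and is not a causal effect. If an effect under adherence is wanted, define it as a separate estimand with a stated method, such as a principal-stratum (complier) or weighting analysis.

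Reconcile the 3% early discontinuation in 3.7 with the expectation in 8.3.

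The cost is a few sentences. Reasons for missed doses are already recorded under 8.4 and 9.3.5, so no new data are needed, and the adherence trigger in 11.4.4 can stay as it is. The change should be made before unblinding.

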11.4.2 Primary Analysis

Treatment and placebo will be compared on the basis of the win-ratio approach as described by Pocock and colleagues:¹¹⁷ In brief, each participant in the treatment group will be compared with each participant in the placebo group. When comparing two participants, the winner will be determined by the first component of the DOOR in which the two participants differ. The following two scenarios will be considered as a tie: (i) when both participants died within 90 days, or (ii) when participants have the same outcomes for all DOOR elements, including length of hospital stay. The win ratio will be calculated by dividing the number of cases in which participants receiving linezolid win compared with the number of cases in which participants receiving placebo win. We will reject the null hypothesis that the win ratio is equal to 1 if the *p*-value is less than 0.05.

Subgroup analyses: For the primary outcome and for all DOOR components separately, we will assess if treatment effects differ by sex (male vs. female), ICU status at baseline (participants on ICU vs. participants not on ICU) and focus of infection (vascular catheter, skin and soft tissue, endocarditis, osteoarticular, pneumonia, other focus, or focus not identified). All subgroup analyses will be exploratory in nature.

